## 6 INTERIM ANALYSIS

An interim analysis was performed after the six participants were enrolled and completed the titration period for each respective titration scheme. A small number of safety tables was agreed on to summarize the available information at that time and the analysis of PK data collected respectively at Week 1 and Week 9 was performed.

## 7 SOFTWARE AND PROGRAMMING SPECIFICATIONS

All datasets, TLFs, and statistical analyses will be generated using SAS, Release 9.4 or higher (SAS Institute Inc., Cary, NC, USA). Computer-generated datasets, table, listing and figure output will adhere to the following specifications:

### 7.1 General Programming Specifications

- One SAS program can create several outputs, or a separate SAS program can be created for each output at the statistical programmer's discretion.
- Each output will be stored in a separate file.
- Output files will be delivered in Word format / rtf format.
- Numbering of TLFs will follow ICH E3 guidance.

### 7.2 Table, Listing, and Figure Format

#### 7.2.1 General

- All TLFs will be produced in landscape format, unless otherwise specified.
- All TLFs will be produced using the Courier New font, size 8.
- The data displays for all TLFs will have a 1.5-inch binding margin on top of a landscape-orientated page and a minimum 1-inch margin on the other 3 sides.
- Legends will be used for all figures with more than 1 variable, group, or item displayed.
- TLFs will be in black and white (no color), unless otherwise specified.
- Specialized text styles, such as bolding, italics, borders, shading, and superscripted and subscripted text, will not be used in the TLFs, unless otherwise specified. On some occasions, superscripts 1, 2, or 3 may be used (e.g.,  $\text{cm}^2$ ,  $\text{C}_{\max}$ ).
- Only standard keyboard characters will be used in the TLFs. Special characters, such as non-printable control characters, printer-specific, or font-specific characters, will not be used. Hexadecimal-derived characters will be used, where possible, if they are appropriate to help display math symbols (e.g.,  $\mu$ ). Certain subscripts and superscripts (e.g.,  $\text{cm}^2$ ,  $\text{C}_{\max}$ ) will be employed on a case-by-case basis.

#### 7.2.2 Headers and Footers

- All outputs should have the following header at the top left of each page:

Beyond Batten Disease Foundation  
Protocol: Batten-1-01

- All outputs should have Page n of N at the top or bottom right corner of each page. TLFs should be internally paginated in relation to the total length (i.e., the page number should appear sequentially as page n of N, where N is the total number of pages in the table).
- The date (date output was generated) should appear along with program name and location as the last footer on each page.

### 7.2.3 Display Titles

- Each TLF should be identified by the designation and a numeral (e.g., Table 14.1.1). ICH E3 recommended numbering will be used. A decimal system (x.y and x.y.z) should be used to identify TLFs with related contents. The title is centered. The analysis population should be identified on the line immediately following the title. The title and table designation are single spaced. A solid line spanning the margins will separate the display titles from the column headers. There will be 1 blank line between the last title and the solid line.

Table x.y.z

First Line of Title

Second Line of Title (if needed)

Analysis Population

### 7.2.4 Column Headers

- Column headers should be displayed immediately below the solid line described above in initial upper-case characters.
- For numeric variables, include “unit” in column or row heading when appropriate.
- Analysis population sizes will be presented for each treatment group in the column heading as (N=xx) (or in the row headings, if applicable). This is distinct from the ‘n’ used for the descriptive statistics representing the number of subjects with available data.

### 7.2.5 Body of the Data Display

#### 7.2.5.1 Table Conventions

- Units will be included where applicable.
- If the categories of a parameter are ordered, then all categories between the maximum and minimum category should be presented in the table, even if n=0 for all treatment groups in a given category that is between the minimum and maximum level for that parameter. For example, the frequency distribution for symptom severity would appear as:

Severity Rating	n
Very Severe	2
Severe	0
Moderate	8
Mild	3

- If the categories are not ordered (e.g., Medical History, Reasons for Discontinuation from the Study, etc.), then only those categories for which there is at least 1 subject represented in 1 or more groups are required.
- As appropriate, an Unknown or Missing category should be added to any parameter for which information is not available for 1 or more subjects.

- P-values should be output in the format: “0.xxx”, where xxx is the value rounded to 3 decimal places. Any p-value less than 0.001 will be presented as <0.001. If the p-value is returned as >0.999 then present as >0.999.
- Unless otherwise specified, tabular display of data for medical history, prior / concomitant medications, and all tabular displays of adverse event data should be presented by the body system, drug class, or SOC in descending order, assuming all terms are coded. Within the body system, drug class and SOC, medical history (by preferred term), drugs (by ATC code), and adverse events (by preferred term) should be displayed in decreasing order. If incidence for more than 1 term is identical, they should then be sorted alphabetically.
- For categorical summaries (number and percentage of subjects) where a subject can be included in more than one category, a footnote will note if the subject should be included in the summary statistics for all relevant categories or just 1 category and the criteria for selecting the criteria.
- Where a category with a subheading (such as system organ class) has to be split over more than one page, output the subheading followed by “(continued)” at the top of each subsequent page. The overall summary statistics for the subheading will only be output on the first relevant page.

#### ***7.2.5.2 Listing Conventions***

- Dates will be printed in SAS® DATE9.format (“DDMMYY: 01JUL2000”).
- All observed time values will be presented using a 24-hour clock HH:MM or HH:MM:SS format (e.g., 11:26 or 11:26:45). Time will only be reported if it was measured as part of the study.
- Units will be included where applicable.

#### ***7.2.5.3 Figure Conventions***

- Unless otherwise specified, for all figures, study visits will be displayed on the X-axis and endpoint (e.g., treatment mean change from Baseline) values will be displayed on the Y-axis.

#### ***7.2.5.4 Footnotes***

- A solid line spanning the margins will separate the body of the data display from the footnotes.
- All footnotes will be left justified with single-line spacing immediately below the solid line underneath the data display.
- Footnotes will be present on all pages of the output. Subject-specific footnotes will be avoided wherever possible.
- Footnotes will be used sparingly and must add value to the table, figure, or data listing.
- The last 2 lines of the footnote section will be a standard source that indicates the name of the program used to produce the data display, date the program was run, and the listing source (or data source for a listing) (e.g., ‘Program: myprogram.sas Listing source: 16.x.y.z’).

## 8 APPENDICES

### 8.1 Imputation Rules for Partial Adverse Event and Medication Dates

The algorithms in [Table 2](#) below should be used for missing dates when needed for determining treatment-emergence of adverse events and prior/concomitant designation of medications. All algorithms assume a comparison to study drug start date and/or study drug end date for categorization.

All dates will be considered to be made of three parts: day, month, and year. Note that if day is non-missing but month is missing, day should be considered missing as well in the algorithms below.

**Table 3. Imputation Rules for Partial Adverse Event/Medication Dates**

AE/Medication Date	Unknown Information	Known Information	Action
Start date	day, month, year	none	Set start date to study drug start date.
Start date	day, month	year	
If year = year of study drug start date, set the date to study drug start date.
 
If year < year of study drug start date, set month and day to December 31st.
 
If year > year of study drug start date, set month and day to January 1st.

Start date	day	month, year	
If year = year of study drug start date and:
 

• month = month of study drug start date, set day to day of study drug start date.

• month < month of study drug start date, set day to last day of month.

• month > month of study drug start date, set day to first day of month.

 
If year < year of study drug start date, set day to last day of month.
 
If year > year of study drug start date, set day to first day of month.

Should the imputed start date based on the rules above be after a known end date for the AE or medication (an end date with no missing date parts), use the end date instead of the date that would be imputed based on the rules above.
			
Medication end date	day, month, year	none	
If ongoing is checked, set the date to study drug end date.
 
If ongoing is not checked, do not impute.

Medication end date	day, month	year	
If year = year of study drug end date, set the date to study drug end date.
 
If year < year of study drug end date, set month and day to December 31st.
 
If year > year of study drug end date, set month and day to January 1st.

Medication end date	day	month, year	
If year = year of study drug end date and:
 
 
• month = month of study drug end date, set day to day of study drug end date.
 
• month < month of study drug end date, set day to last day of month.
 
• month > month of study drug end date, set day to first day of month.
 
 
If year < year of study drug end date: set day to last day of month.
 
If year > year of study drug end date: set day to first day of month.


Should the imputed end date come before the start date (either fully known or imputed) then use the start date instead of the date that would be imputed based on the rules above.
			

Should the imputed end date come after the date of the subject's death or after the subject's End of Study (if applicable), then use the date of death or End of Study date instead.

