## **6.6 Concomitant Therapy**

Any medication the subject takes other than the study drug is considered a concomitant medication. All concomitant medications must be recorded in the eCRF. The following information must be recorded in the eCRF for each concomitant medication: generic name, route of administration, start date, stop date, dosage, and indication. If possible, subjects should try to remain on the pre-study dose(s) of concomitant medication(s) throughout the study. Any changes in the dosage or regimen of a concomitant medication must be recorded in the eCRF.

At screening, subjects will be asked what medications they have taken during the last 3 months. At each subsequent study visit, subjects will be asked what concomitant medications they are currently taking.

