#### 5.1.1 Adverse Events

**Non-treatment emergent adverse events** (AEs) will be collected from the time the subject screened into the study (date of signature of informed consent) until first administration of study drug.

Thereafter, all AEs are **treatment-emergent adverse events** (TEAEs) and will be recorded until the end of study visit has been performed. In all outputs, AEs with start date(time) on or after the study drug start date(time) will be considered as TEAEs (i.e., TEAE designation will be programmatically derived based on dates; eCRF checkbox for TEAE will not be used). In case it is impossible to determine whether an AE is treatment-emergent or not (i.e., AE occurs on day 1 but time is unknown), the AE will be considered a TEAE.

Partial start dates of AEs will be imputed according to section [8.1](#) for the determination of non-treatment emergent and treatment-emergent designations.

AEs will be coded based on the Medical Dictionary for Regulatory Activities (MedDRA) latest version available before the database lock. National Cancer Institute's Common Terminology Criteria for Adverse Events (CTCAE) v5.0 will be used for the grading of AEs by the investigators.

For summary tables, AEs with relatedness "Definite", "Probable", and "Possible" will be considered as "Related", AEs with relatedness "Unrelated" and "Unlikely" will be considered "Not Related" and AEs with relatedness "Not Applicable" will be reported as such. AEs with missing relatedness assessment will be considered as "Related" for summary tables and will be footnoted in applicable tables; listings will present relatedness data as collected (i.e., missing).

AEs with missing seriousness assessment will be considered as "Serious" for summary tables; listings will present seriousness data as collected (i.e., missing). Should AEs with missing seriousness be present at time of reporting, these will be footnoted in applicable serious adverse event tables.

AEs with missing severity assessment will be considered as "Grade 3" for summary tables; listings will present severity data as collected (i.e., missing). Should AEs with missing severity be present at time of reporting, these will be footnoted in applicable adverse event tables.

An overall summary of AEs will be produced, including counts and percentages of subjects with any incidence of:

1. AEs (including non-treatment emergent AEs),
2. TEAEs,

3. Non-serious TEAEs,
4. Serious TEAEs (TESAEs),
5. Related TEAEs,

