## 5.8 Prior and Concomitant Medications

Prior and concomitant medications will be coded using the latest version of World Health Organization Drug Dictionary (WHODD) available before the database lock.

Prior medications are those which have been identified to have been discontinued prior study drug start date (i.e., taken exclusively before treatment start). Concomitant medications are those which have been identified to have been taken at any point on or after the study drug start date. If it is not possible to determine whether a medication is prior or concomitant, it will be assumed to be concomitant.

Partial start and end dates of medications will be imputed according to section [8.1](#) for the determination of prior and concomitant designations.

The incidence of concomitant medication use will be summarized for the Safety Population by WHODD anatomic therapeutic chemical (ATC) Level 2 classification (i.e., therapeutic main group) and preferred name. A subject will be counted only once at each level of reporting. Prior medication use will only be listed.

Prior and concomitant medication data will be listed.

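### SAP 8.1 Table 3 turns one narrow type of record (start month unknown, partial end date wholly before first dose) into a TEAE or a concomitant medication

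*SAP*

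**What the plan says.** **Start dates (SAP 8.1, Table 3).** If the start date is fully missing, the action is "Set start date to study drug start date". If only the year is known and it is the first-dose year, the action is "set the date to study drug start date".

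**Safeguard.** It opens "Should the imputed start date based on the rules above be after a known end date for the AE or medication (an end date with"; the condition and action then read "an end date with no missing date parts), use the end date instead of the date that would be imputed based on the rules above". It covers AEs and medications, but only when the end date is complete.

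**Medication end dates.** A partial end date is imputed, for example to the last day of its month when it falls before the month of last dose. Then: "Should the imputed end date come before the start date (either fully known or imputed) then use the start date instead". Table 3 has no end-date rule for AEs.

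**How the dates are used.** SAP 5.1.1 derives TEAE status by program from the start date alone. SAP 5.8 calls a medication prior if it stopped before the study drug start date, and concomitant if it was taken on or after that date. It adds: "If it is not possible to determine whether a medication is prior or concomitant, it will be assumed to be concomitant". SAP 5.2.2 uses the same imputation rules to place seizure AEs in time intervals.

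**The concern.** An end month or year that lies wholly before first dose settles the question: the event or the drug was over before treatment began. Table 3 does not use that information in the case described. It invents a start on the first-dose date and lets the invention stand. For medications it also overwrites an end date that had been imputed sensibly.

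For medications this departs from SAP 5.8, where the concomitant default is kept for records whose status cannot be determined.

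Three outputs are exposed:

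- TEAE incidence, which is part of the primary endpoint.
- The concomitant medication table. It is the only medication summary, because prior medications are only listed.
- The seizure counts. A pre-treatment seizure AE with such dates would move from the *Pre-treatment* interval to *Baseline to month 3*.

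**Working it through.** **Inputs.** The rules are those of SAP 8.1 Table 3, 5.1.1 and 5.8. The calendar dates are assumed for illustration: first dose D = 15 May 2022, last dose 1 Feb 2024. The sample size is six (SAP 2.2).

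**Definitions.** S is the imputed start. L is the latest date consistent with the known parts of the end date.

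- As written: S = D if the start is missing, or is year-only in the year of D. S is replaced by the end date only if the end date is complete and earlier than S. For medications, final end = the later of the imputed end and S.
- AE: TEAE if S ≥ D. Here S = D with no clock time, and SAP 5.1.1 counts a Day 1 event of unknown time as a TEAE.
- Medication: concomitant if the final end ≥ D.
- With the start capped: S is replaced by L whenever L < S.

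| Start recorded | End recorded | L | S as written | Medication end as written | Status as written | S with cap | Status with cap |
|---|---|---|---|---|---|---|---|
| missing | Apr 2022 | 30 Apr 2022 | 15 May 2022 | 30 Apr, moved to 15 May 2022 | TEAE / concomitant | 30 Apr 2022 | pre-treatment / prior |
| missing | 2021 | 31 Dec 2021 | 15 May 2022 | 31 Dec 2021, moved to 15 May 2022 | TEAE / concomitant | 31 Dec 2021 | pre-treatment / prior |
| 2022 | Apr 2022 | 30 Apr 2022 | 15 May 2022 | 30 Apr, moved to 15 May 2022 | TEAE / concomitant | 30 Apr 2022 | pre-treatment / prior |
| missing or 2022 | 10 Apr 2022 | 10 Apr 2022 | 10 Apr 2022 | 10 Apr 2022 | pre-treatment / prior | unchanged | unchanged |
| 2021 | Apr 2022 | 30 Apr 2022 | 31 Dec 2021 | 30 Apr 2022 | pre-treatment / prior | unchanged | unchanged |
| Mar 2022 | Apr 2022 | 30 Apr 2022 | 31 Mar 2022 | 30 Apr 2022 | pre-treatment / prior | unchanged | unchanged |
| missing | May 2022 | 31 May 2022 | 15 May 2022 | 31 May 2022 | TEAE / concomitant | unchanged | unchanged |

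Rows 1 to 3 are the error. Comparing rows 1 and 4 isolates the cause: losing only the day of the end date reverses the status, although both end dates precede first dose. The last row is truly undeterminable, and the conservative default rightly stays.

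The result does not depend on the time of year. With D = 20 Jan 2022, a missing start and an end of Dec 2021 give S = 20 Jan 2022 (TEAE / concomitant) as written, and S = 31 Dec 2021 (pre-treatment / prior) with the cap.

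**Seizures.** The imputed start is Day 1, inside the Day 1 to 90 interval. SAP 5.2.2 also compares clock times on Day 1. An imputed date has none, so I assume that the SAP 5.1.1 default carries over.

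**Weight of one record.** 1/6 = 16.7 percentage points, if the subject has no other event in that row. SAP 5.1.1 counts each subject once per category.

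**The case against.** **Imputation applies only when needed.** SAP 8.1 says that the algorithms are for use where they are needed to settle status. One could argue that an end date of April 2022 already identifies a medication as stopped before a May first dose, so nothing is imputed. That is tenable for medications, but the SAP does not say it, and the end-date rule expressly lets an imputed start override an end. It does not help AEs, whose status is programmed from start dates.

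**The choice is deliberate and conservative.** The parentheses in both override rules look considered. SAP 5.1.1 also defaults missing relatedness to related, missing seriousness to serious and missing severity to Grade 3. The direction of the error does fit that pattern. But those defaults fill a gap where nothing was recorded; here a recorded date contradicts the default.

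**Such records are rare.** This largely stands. AEs are recorded only from consent, and the planned screening window is Days -42 to -1, so an AE with no start month but a pre-dose end month is unlikely. Protocol 6.6 requires start and stop dates for medications, and Protocol 9.2 repeats queries until they are resolved. Recalled medication history is the more plausible source: "At screening, subjects will be asked what medications they have taken during the last 3 months".

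**The SAP 5.1.1 wording.** A reader might infer that the rule also contradicts SAP 5.1.1, which begins a default with "In case it is impossible to determine whether an AE is treatment-emergent or not". The text does not support this. The sentence goes on to explain itself by a Day 1 event with an unknown clock time, so it says nothing about partial end dates. Only SAP 5.8 supports the argument from stated intent.

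**Conclusion.** The point holds for one record type only. The start must be fully missing, or year-only in the first-dose year, and the end must be partial with its known month or year wholly before first dose. Read literally, Table 3 then makes an AE treatment-emergent and a medication concomitant when the record itself rules that out.

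Three stronger readings are not supported:

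- That Table 3 ignores every partial end date before dosing. A start month known to be before first dose, or an earlier known start year, leads to the right status, as does any complete end date. A partial medication end date is imputed and then overwritten, not ignored.
- That a misclassification rate can be stated. One can work out how often a month-only end falls wholly before dosing, but that is conditional on the record already having an unknown start and a partial end. The documents give no count of such records.
- That the overall TEAE figure will shift by 16.7 points. It shifts only for a subject with no other TEAE. Treatment runs to Week 78 and beyond, and SAP 5.2.2 has diary seizures reported as AEs too, so the overall row is unlikely to move. A sparse preferred-term or medication row could.

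The error is minor and conservative in direction, but the rule demonstrably gives the wrong answer and is cheap to correct. The conclusion rests on a literal reading of Table 3; the dates in the example are assumed.

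**What to change.** In SAP 8.1 Table 3, replace the start-date safeguard with: *If the latest date consistent with the known parts of the end date is before the imputed start date, set the start date to that latest date.* For a complete end date this reduces to the present rule.

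Leave the end-date override as it is. Once the start is capped, the imputed end no longer precedes it in the affected records, so the override does not fire. Restricting the override to fully known starts is unnecessary and would do harm. Take first dose in 2022, last dose 15 Apr 2024, and a medication with start May 2024 and end 2024. The start becomes 1 May 2024 and the end 15 Apr 2024. The cap does not fire, because the latest possible end is 31 Dec 2024, and without the override the end would precede the start.

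The cost is one sentence and a few lines of derivation code before database lock, with no new data. The downside is a slightly less conservative default, limited to records whose own end date excludes onset or use on treatment. If the end month is the first-dose month, the present default still applies.
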